6.2.2. Study Period

Assessments and events (e.g., study withdrawal) will be classified according to the time of occurrence relative to the study intervention period.

Study Phase	Definition
Pre-Intervention	Reference Day \leq Previous Day of Dosing Start Date in Period 1
Period 1	Dosing Start Date in Period 1 $<$ Reference Day \leq Previous Day of Dosing Start Date in Period 2
Period 2	Dosing Start Date in Period 2 \leq Reference Day

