5.3. Participant and Study Completion

A participant is considered to have completed the study if he/she has completed all phases of the study including the follow-up visit.

The end of the study is defined as the date of the last visit of the last participant in the study.

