9.2.1. Time Period and Frequency for Collecting AE and SAE Information

- All SAEs will be collected from the start of treatment until the follow-up visit at the time points specified in the SoA (Section 2). However, any SAEs assessed as related to study participation (e.g., study treatment, protocol-mandated procedures, invasive tests, or change in existing therapy) or related to a GSK product will be recorded from the time a subject consents to participate in the study.
- All AEs will be collected from the start of treatment until the follow-up visit at the time points specified in the SoA (Section 2).
- Medical occurrences that begin before the start of study treatment but after obtaining informed consent will be recorded on the Medical History/Current Medical Conditions section of the eCRF not the AE section.
- All SAEs will be recorded and reported to the sponsor or designee immediately and under no circumstance should this exceed 24 hours, as indicated in [Appendix 6](#). The investigator will submit any updated SAE data to the sponsor within 24 hours of it being available.
- Investigators are not obligated to actively seek AEs or SAEs in former study participants. However, if the investigator learns of any SAE, including a death, at any time after a participant has been discharged from the study, and he/she considers the event to be reasonably related to the study treatment or study participation, the investigator must promptly notify the sponsor.
- The method of recording, evaluating, and assessing causality of AEs and SAEs and the procedures for completing and transmitting SAE reports are provided in [Appendix 6](#).

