1.2. Study Design

Overview of Study Design and Key Features													

The diagram illustrates the study design timeline. It begins with a 'Screening' phase from Week -4 to Day 1, including 'Hgb Stability Check' at Weeks -4, -2, and Day 1. This is followed by 'Randomize Day 1'. The study then enters two 28-day 'Treatment Periods'. Treatment Period #1 involves 'rhEPO' and 'Daprodustat' from Day 1 to Day 28, with a 'Dose Tracer' at Day 15 and 'Assess RBC Fe Crossover' at Day 29. Treatment Period #2 involves 'Daprodustat' and 'rhEPO' from Day 29 to Day 56, with a 'Dose Tracer' at Day 43 and 'Assess RBC Fe' at Day 57. The study concludes with a 'Follow-Up' phase starting at Day 57.
													

Design Features
	
This study will be a randomized, repeat dose, open label, two period cross-over study in adult, male and female participants with anemia associated with chronic kidney disease who are not on dialysis currently treated with stable doses ($\leq 50\%$ change in 4-weekly dose) for at least 8 weeks prior to and including the screening period, of rhEPO (i.e., epoetin alfa or darbepoetin alfa).
 
 • There will be a 4-week screening period in order to confirm that participants have stable Hgb levels and to assess entry criteria • A 28-day Treatment Period 1 for incorporation of iron into erythrocytes while on randomized study treatment • A 28-day Treatment Period 2 for a second incorporation of iron into erythrocytes while on randomized study treatment • A follow-up visit 14 ± 3 days after completing treatment. 												

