4.4.2. Adverse Events

Adverse events analyses including the analysis of adverse events (AEs), Serious AEs (SAEs) and other significant AEs will be based on GSK Core Data Standards. An overview summary of AEs, including counts and percentages of participants with any AE, AEs related to study intervention, SAEs related to study intervention, fatal SAEs, and fatal SAEs related to study intervention will be produced. Adverse events will be coded using the standard Medical Dictionary for Regulatory Affairs (MedDRA dictionary). A summary of number and percentage of participants with any adverse events by maximum severity will be produced. A separate summary will be provided for

study intervention-related AEs. A study intervention-related AE is defined as an AE for which the investigator classifies the possible relationship to study intervention as “Yes”. A worst-case scenario approach will be taken to handle missing relatedness data, i.e. the summary table will include events with the relationship to study intervention as ‘Yes’ or missing. The summary table will be displayed by PT only. All SAEs will be tabulated based on the number and percentage of participants who experienced the event. Separate summaries will also be provided for study intervention-related SAEs. The summary tables will be displayed by PT and SOC. A study intervention-related SAE is defined as an SAE for which the investigator classifies the relationship to study intervention as “Yes”. A worst-case scenario approach will be taken to handle missing data, i.e. the summary table will include events with the relationship to study intervention as ‘Yes’ or missing. Summaries and listings of adverse events will include treatment sequence. A listing of AEs that occur during Follow-up will be provided. AEs leading to permanent discontinuation of study intervention and study intervention related AEs leading to permanent discontinuation of study intervention will be listed.

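### Minor error in SAP 6.2.2 and 6.2.6: the first dosing date is in no phase, participants who never start Period 2 cannot be placed, Period 2 has no end, and partial AE dates are imputed without the Period 2 start

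*SAP*

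**What the plan says.** SAP 6.2.2 states its scope as follows: "Assessments and events (e.g., study withdrawal) will be classified according to the time of occurrence relative to the study intervention period". It then defines three phases:

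- Pre-Intervention ends on the day before Period 1 dosing starts.
- Period 1 has the lower bound "Dosing Start Date in Period 1 $<$ Reference Day" and the upper bound "Previous Day of Dosing Start Date in Period 2".
- Period 2 covers every day on or after the Period 2 dosing start. It has no upper bound, and no Follow-up row comes after it.

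The rest of the plan does have a follow-up phase. SAP 1.2 schedules it: "A follow-up visit 14 ± 3 days after completing treatment". Protocol 9.2.1 collects events through it: "All AEs will be collected from the start of treatment until the follow-up visit". SAP 4.4.2 promises an output for it: "A listing of AEs that occur during Follow-up will be provided". Protocol 5.3 makes it a condition of completion: "A participant is considered to have completed the study if he/she has completed all phases of the study including the follow-up visit".

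SAP 6.1.1 summarizes withdrawals and their reasons overall and by study period. SAP 6.2.6 lets imputed partial dates be used to slot data into phases. Its AE rule sets a missing start day either to the start of study intervention, when month and year match and no earlier full stop date contradicts this, or to the 1st of the month. The Period 2 start is not mentioned.

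**The concern.** A phase rule should put each date in exactly one phase. This one leaves a gap at the first dosing date. It has no answer for a participant without a Period 2 start date, and it merges post-treatment time with treatment time. The second gap matters for the rule's own example, study withdrawal: Protocol 8.1 withdraws anyone who discontinues treatment, so withdrawals during Period 1 are foreseen.

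The imputation rule is a further difficulty in a crossover. The period identifies the treatment, so moving a Period 2 onset back to the 1st of the crossover month can move the event to the other treatment. With about 12 evaluable participants planned, a single misplaced withdrawal or AE would be visible in any display by period.

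**Working it through.** **Inputs.** Two 28-day treatment periods, crossover at Day 29 and follow-up at Day 70 ± 3 (Protocol section 2, SAP 1.2). Assumption for the count: the last treatment day is Day 56. Write D1 and D2 for the two dosing start dates.

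**Step 1: apply 6.2.2 literally.** Pre-Intervention is date ≤ D1 − 1; Period 1 is D1 < date ≤ D2 − 1; Period 2 is D2 ≤ date.

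| Participant | Pre | Period 1 | Period 2 | Follow-up | No phase |
|---|---|---|---|---|---|
| Completer, Day −28 to Day 70, as written | 28 | 27 | 42 | – | 1 (Day 1) |
| Same, with the corrections below | 28 | 28 | 28 | 14 | 0 |
| Last dose Day 20, follow-up Day 20 + 14 = Day 34, as written | 28 | 0 | 0 | – | 34 |
| Same, with the corrections below | 28 | 20 | 0 | 14 | 0 |

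The strict bound looks like a slip: the Period 2 row uses ≤, and SAP 6.2.3 makes the intervention start study day 1.

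**Step 2: post-treatment share of literal Period 2.**

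- Days 29 to 70 are 70 − 29 + 1 = 42 days. Days 57 to 70 are 14 days. 14/42 = 33%.
- Over the ±3-day window: 11/39 = 28% to 17/45 = 38%.
- If the Day 57 visit is counted as the end of treatment: 13/42 = 31%.

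These are shares of calendar days, not of events.

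**Step 3: apply the 6.2.6 missing-start-day rule, then 6.2.2.** Example: D1 is 10 March and D2 is 7 April. An AE recorded only as April is imputed to 1 April and falls in Period 1, even if it began on 20 April.

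All 365 start dates of a non-leap year were enumerated, with onset spread evenly over the 28 days of Period 2 and no full stop date before treatment start. That gives 365 × 28 = 10,220 onset days:

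- As written: 5,294 go to Period 1 (51.8%), 54 to no phase (0.5%) and 4,872 to Period 2 (47.7%).
- With the strict bound made inclusive: (5,294 + 54)/10,220 = 52.3% go to Period 1.
- By crossover date, with the inclusive bound: from 0 of 28 days (crossover on the 1st) to 28 of 28 (the 2nd–3rd of a 30-day month or the 2nd–4th of a 31-day month), median 15.

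The strict bound and the imputation also compound. Of Period 1 onsets on Days 2–28, 5,319 of 9,855 (54.0%) are imputed to the first dosing date, which as written is in no phase.

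**Step 4: which displays depend on phase.** Disposition by study period (6.1.1) and the Follow-up AE listing (4.4.2) do. Visit summaries use nominal visits (6.2.4), and the primary endpoint is computed from nominal-day measurements (4.2.1). For AEs the SAP says only "Summaries and listings of adverse events will include treatment sequence"; it specifies no AE table by period.

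**The case against.** Several points on the other side are sound.

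- **Disposition.** 6.1.1 also requires a study intervention status summary, which already separates treatment completers from those who discontinued treatment early. A completer who misses the follow-up visit, and is recorded as withdrawn, would therefore be mixed with on-treatment withdrawals only in the by-period withdrawal display.
- **Follow-up listing.** Treatment stop dates are recorded (Protocol 7.6) and used for exposure (SAP 4.4.1). A programmer could find Follow-up AEs from those dates without 6.2.2.
- **Partial dates.** 6.2.6 shows them as captured in listings and makes imputation for slotting optional. Their number is unknown.
- **Evident intent.** The first-day gap and the missing Period 2 default have an obvious intended reading. SAP section 1 places further data-handling conventions in the OPS, which is not available here and may fill the omissions.

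These points limit the size but do not remove the error. The OPS would have to contradict an explicit inequality, and the stated rule cannot place the event it names as its example.

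A reader might infer from the percentages that half of Period 2 AEs go to the wrong treatment, or that a third of Period 2 events are misclassified. The documents support neither: the first figure applies only to AEs with a missing start day, and the second counts days. Nor do they support any effect on the iron absorption comparison.

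The opposite inference, that the crossover balance makes misplacement harmless, is also unsupported. Moving events to the other treatment's period would dilute a treatment difference in any by-period display, and withdrawals can upset the planned three per sequence.

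**Conclusion.** Minor, and wrong as written. Three bounds in 6.2.2 fail on a plain reading: the first dosing date, participants who never start Period 2, and the open-ended Period 2. The partial-date rule in 6.2.6 ignores the boundary that separates the treatments.

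The consequences reach disposition by period, the Follow-up AE listing and any display by phase. The primary and secondary endpoints, and overall and by-sequence AE counts, are unaffected.

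The first-day gap rests on explicit wording. The missing Follow-up row and Period 2 default are omissions that the OPS may address. The 52% is illustrative: it assumes uniform onset and start dates and a missing start day, and it feeds no AE table that the SAP specifies.

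**What to change.** - **(a)** Change < to ≤ at the Period 1 lower bound.
- **(b)** For disposition, classify the withdrawal of anyone who never starts Period 2 as Period 1.
- **(c)** Give the last treatment period one defined end date, used consistently, so that Day 57 has a single status. Add a Follow-up row after it.
- **(d)** For partial AE dates, compare the known month or year with every phase boundary: Period 1 start, Period 2 start and end of treatment. Use a full stop date where it settles the phase; otherwise flag the phase as undetermined in the listing.

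In (d), comparison with the two period starts alone is not enough. Once a Follow-up row exists, imputation to the 1st would still send 74.9% of Day 57–70 onsets with a missing start day to Period 2 (76.8% of Day 58–70 onsets if Period 2 ends on Day 57).

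The cost is SAP wording and minor programming, with no new data. The flag will be common among partially dated AEs: a calendar month can lie wholly inside a 28-day Period 2 only if it is a 28-day February, so the month alone almost never settles a Period 2 onset. The fix makes that uncertainty visible; it does not place every such AE.

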6.2.3. Study Day and Reference Dates

The safety reference date is the study intervention start date and will be used to calculate study day for safety measures.

The efficacy reference date is the study intervention start date and will be used to calculate study day for efficacy measures and baseline characteristics, as well as efficacy durations.

The study day is calculated as below:

- Assessment Date = Missing \rightarrow Study Day = Missing
- Assessment Date $<$ Reference Date \rightarrow Study Day = Assessment Date – Ref Date
- Assessment Date \geq Reference Date \rightarrow Study Day = Assessment Date – Ref Date + 1

6.2.4. Assessment Window

For data summaries by visit, scheduled visits with nominal visit description will be displayed. Unscheduled visits will not be displayed or slotted into a visit window but will be included in the derivation of worst-case post baseline assessment. All un-scheduled visits will be displayed in listings, as appropriate.

6.2.5. Multiple measurements at One Analysis Time Point

When triplicate ECG assessments are taken, mean of the measurement will be calculated first and summary statistics will be based on the calculated mean. This will apply to both baseline and post baseline assessments.

For lab tests on a study day, if more than one assessment is taken on the same day, the test from a central lab will be taken over the test from a local lab. If multiple assessments are taken from the same type of lab, the worst case will be used.

6.2.6. Handling of Partial Dates

Element	Reporting Detail				
General	
 • Partial dates will be displayed as captured in participant listing displays. • However, where necessary, display macros may impute dates as temporary variables for sorting data in listings only. In addition, partial dates may be imputed for ‘slotting’ data to study phases or for specific analysis purposes as outlined below. • Imputed partial dates will not be used to derive study day, time to onset or duration (e.g., time to onset or duration of adverse events), or elapsed time variables (e.g., time since diagnosis). 				
Adverse Events	
 • Partial dates for AE recorded in the CRF will be imputed using the following conventions: 
 
 Missing start day	 
If study intervention start date is missing (i.e. participant did not start study intervention), then set start date = 1st of month.
 
Else if study intervention start date is not missing:
 
 ○ If month and year of start date = month and year of study intervention start date, then 
 ▪ If stop date contains a full date and stop date is earlier than study intervention start date, then set start date= 1st of month. ▪ Else set start date = study intervention start date. 
Else set start date = 1st of month.
 	
 
 Missing start day and month	 
If study intervention start date is missing (i.e. participant did not start study intervention), then set start date = January 1.
 	
 
 	Missing start day	
If study intervention start date is missing (i.e. participant did not start study intervention), then set start date = 1st of month.
 
Else if study intervention start date is not missing:
 
 ○ If month and year of start date = month and year of study intervention start date, then 
 ▪ If stop date contains a full date and stop date is earlier than study intervention start date, then set start date= 1st of month. ▪ Else set start date = study intervention start date. 
Else set start date = 1st of month.
	Missing start day and month	
If study intervention start date is missing (i.e. participant did not start study intervention), then set start date = January 1.

Missing start day	
If study intervention start date is missing (i.e. participant did not start study intervention), then set start date = 1st of month.
 
Else if study intervention start date is not missing:
 
 ○ If month and year of start date = month and year of study intervention start date, then 
 ▪ If stop date contains a full date and stop date is earlier than study intervention start date, then set start date= 1st of month. ▪ Else set start date = study intervention start date. 
Else set start date = 1st of month.
				
Missing start day and month	
If study intervention start date is missing (i.e. participant did not start study intervention), then set start date = January 1.
				

Element	Reporting Detail	
		
Else if study intervention start date is not missing:
 
If year of start date = year of study intervention start date, then
 
If stop date contains a full date and stop date is earlier than study intervention start date, then set start date = January 1.
 
Else set start date = study intervention start date.
 
Else set start date = January 1.

	Missing end day	A '28/29/30/31' will be used for the day (dependent on the month and year).
	Missing end day and month	No Imputation
	Completely missing start/end date	No imputation
Concomitant Medications/ Medical History	
 Partial dates for any concomitant medications recorded in the CRF will be imputed using the following convention: 	
	Missing start day	
If study intervention start date is missing (i.e. participant did not start study intervention), then set start date = 1st of month.
 
Else if study intervention start date is not missing:
 
 ○ If month and year of start date = month and year of study intervention start date, then 
 ▪ If stop date contains a full date and stop date is earlier than study intervention start date, then set start date= 1st of month. ▪ Else set start date = study intervention start date. 
Else set start date = 1st of month.

	Missing start day and month	If study intervention start date is missing (i.e. participant did not start study intervention), then

Element	Reporting Detail	
		
set start date = January 1.
 
Else if study intervention start date is not missing:
 
 ○ If year of start date = year of study intervention start date, then 
 ▪ If stop date contains a full date and stop date is earlier than study intervention start date, then set start date = January 1. ▪ Else set start date = study intervention start date. 
Else set start date = January 1.

	Missing end day	A '28/29/30/31' will be used for the day (dependent on the month and year).
	Missing end day and month	A '31' will be used for the day and 'Dec' will be used for the month.
	Completely missing start/end date	No imputation

6.2.7. Early PK Access Key Activities

NA

Trademarks

Trademarks of the [GlaxoSmithKline / ViiV Healthcare] Group of Companies
HARP

Trademarks not owned by the [GlaxoSmithKline / ViiV Healthcare] Group of Companies
SAS

